7. STUDY PROCEDURES AND SCHEDULE

7.1 STUDY SCHEDULE

7.1.1. Screening

AIM 1: Individual interviews with patients: A nurse will assess eligibility among patients that they are checking in for regularly scheduled appointment and explain that we are conducting a study and describe the purpose of the study. Patients will then be asked if they are willing to complete screening questions to assess eligibility. If eligible, the subject will be asked to choose from several dates to participate in an interview. No screening data will be kept for the purpose of the study unless subjects consent to participation. All study related activities and study data collection will occur only AFTER verbal consent is obtained. We are requiring that the interviews are audiotaped and therefore will let potential participants know that at the time they are screened to offer them an opportunity to decline at that time. However, we will again explain that the interview will be audio taped prior to beginning the interview during the verbal consent process at which time they will have another chance to opt out.

Key informant interviews with providers will be conducted in aim 1 to inform the design of the intervention. Health care workers will be told about the study at a group meeting. It will be made clear to them that participation is voluntarily, and they don't have to participate. A research coordinator will follow up with a phone call to schedule interviews. We will obtain verbal consent. Once the intervention components are finalized, we will conduct a pilot study in one OPC with 16 patients randomized to ARM 1 and 3 of the proposed RCT. Screening and recruitment will follow the approach described in Aim 2 below.

AIM 2: Patient recruitment: Nurses will assess smoking status at the time patients register for their visit. If patients are current smokers, nurses will briefly describe the RCT study and explain that those patients who are interested in participating will be screened for eligibility. Patients who refuse to be screened or who do not meet eligibility criteria will be provided a cessation brochure. Those patients who meet eligibility criteria will be introduced to the onsite RA. The RA will read the consent and the patient will sign a paper version in the clinic. Once they consent, the RA will conduct the baseline survey and randomize patients before their provider visit. The consent process and survey will take about 30-40 minutes.

Healthcare provider recruitment: Health care workers will be told about the study at a group meeting. It will be made clear to them that participation is voluntarily and they don't have to participate. This will be repeated at the time of the consent process. All health workers are eligible. Research staff will follow-up to contact providers and staff to make appointments for to administer the baseline and follow up surveys. Written consent will be obtained at the time of the baseline survey. Health care providers who participate in surveys will be asked to complete the survey again at 12 months post intervention. We are requiring that the interviews are audiotaped, as described above. We will let potential participants know about the audio taping at the time we describe the study to offer them an opportunity to decline at that time if that is a reason they do not want to participate. However, we will again explain that the interviews will be audio taped prior to beginning at which time they will have another chance to opt out.

AIM 3: Provider interviews. Health care workers who were enrolled in AIM 2 will have been consented to also participate in interviews and surveys post intervention to assess the implementation process.

AIM 4: Patient recruitment: non-smokers will be recruited using the methods described for recruiting smokers as detailed in AIM 2 patient recruitment above.

7.1.2 Enrollment/Baseline.

AIM 1: Patient Interviews: We will confirm eligibility and then ask participants to choose an interview date. Participants will be offered an explanation of the purpose of the study, given a one-page description with a number to call if they have additional questions. We will obtain verbal consent at the time of the interview immediately before it begins.

AIM 1 and 3: Provider surveys and KIs: We will confirm eligibility which only includes that the provider is currently working at the OPC. Providers will be asked to provide verbal consent for preintervention interviews and written consent to enroll in the longitudinal assessment (surveys and KIs). The initial survey and KI will occur at baseline and then they both will be repeated at 12 months. A separate survey to assess sustainability will be conducted at 18 months, for which written consent will be obtained before administering the survey.

AIM 2 RCT and AIM 4: Nurses will assess smoking status at the time patients register for their visit. Nurses will describe the study and explain that those patients who are interested in participating will be screened for eligibility. Patients who refuse to be screened or who do not meet eligibility criteria will be provided a cessation brochure. Those patients who meet eligibility criteria will be introduced to the study RA. The RA will obtain written consent. Once they consent, the RA will conduct the baseline survey and randomize patients. The consent process and survey will take about 30-45 minutes.

7.1.3 Study visits

AIM 1 Patients: The first and final visit for patients in AIM 1 is the interview. Patients enrolled in the AIM 1 pilot study will complete the same study visits as described below in Aim 2.

AIM 1-3 Providers: Provider visits include in person KIs for Aim 1 (n=28). For Aim 2 providers will be asked to complete a baseline survey (n=98) and KIs (n=28) across the 13 study OPCs. For AIM 3 we will repeat the survey and KIs at 12 months, and separately conduct a sustainability survey at 18 months.

AIM 2 RCT and AIM 4: Patients will be asked to complete a baseline, 3-, and 6-month survey. The baseline survey will take place in person. All other surveys will be conducted by telephone, 3 and 6-months. At 6-months follow up patients who report smoking abstinence will be asked to come in person to the OPC and will complete a carbon monoxide test at the OPC to validate self-report.

7.1.4. Methods and Procedures.

AIM 1: Patient Interviews. Experienced interviewers from our partnering institution in Vietnam (i.e., Institute for Social and Medical Studies, ISMS) will conduct these interviews (n=24). The number of interviews will depend on reaching saturation.

AIM 1-3: Health care provider surveys and interviews. All interviews and surveys will be administered by experienced ISMS staff. The interviews will be digitally recorded, transcribed and translated and stored as described above. We will not conduct the interviews if participants refuse to have the interview recorded. Surveys are administered using REDCap on iPads at baseline and 12 months and 18 months post intervention.

AIM 2 RCT and AIM 4: All patient surveys are administered using REDCap. The baseline patient survey is conducted in person at the time of enrollment. All other surveys will be conducted by telephone, 3- and 6- months. At 6-months follow up patients who report smoking abstinence will be asked to come in person to the OPC and will complete a carbon monoxide test at the OPC to validate self-report. The CO test involves the patient blowing through a small cardboard tube into a small handheld monitor which measures the amount of CO expired. A positive test (i.e., still smoking) will be defined as >10ppm. The CO test visit will take about 20 minutes and the findings will be recorded in REDCap.

7.1.5. Withdrawal/Early termination visit. The clinical site, patients and providers may withdraw from the study at any time.

7.1.6. Unscheduled Visit. For the AIM 2 RCT, unscheduled visits to the nurse counselor will be discouraged. All provider surveys and key informant interviews will be scheduled.

7.1.7. Participant access to study agent at study closure. We will not be providing NRT after the study closes.

7.1.8. Prohibited medications. There are no prohibited medications. Patients will be able to continue with all of their current medications.

7.1.9. Final Study Visit.

Patients: the visit at 6 months post enrollment is a telephone survey followed by in-person CO confirmation test if the patient reports that they have stopped smoking. We will remind patients about the Quitline service that they can access for additional support and give them the number to call.

Providers: the visit at 18 months post enrollment is an in-person survey to assess sustainability.

8. ASSESSMENT OF SAFETY

8.1 SPECIFICATION OF SAFETY PARAMETERS. This is a minimal risk study. Patients enrolled in the RCT will receive a standard care behavioral intervention from their health care providers (brief counseling plus Quitline counseling) vs provider brief counseling plus the addition of 6 sessions of nurse delivered counseling vs brief physician counseling + multisession nurse delivered counseling +NRT. Eligibility for NRT will be assessed at the time study eligibility is assessed and prior to enrollment. It is important to note that the nicotine gum is an over-the-counter medication, proven safe, with minimal potential side effects. In addition, there are no significant interactions between NRT and HIV treatments (<http://www.hivdruginteractions>). Patients with a recent history of MI (four weeks), uncontrolled hypertension, arrhythmia, or worsening angina pectoris will not be eligible to enroll. Potential side effects related to NRT will be assessed by the nurse counselor at each counseling visit and reported in the tracking form that counselors use to document visits. The length of treatment with NRT (6 weeks) will generally coincide with those visits. At the time of enrollment participants in the nicotine gum arm will be told of the common side effects (e.g., Rash, mouth, tooth, or jaw problems, palpitations) they may experience and asked to report any problems to the nurse and/or doctor in the clinic or to call the contact number on the consent form. They will also be told how to reduce the likelihood of common side effects, including not smoking while using the gum. Counselor training will include information about potential side effects and to explore potential reasons for side effects and suggest ways to reduce side effects. The PIs will be contacted within 24 hours if the physician or counselor believes there is an AE or SAE, otherwise, forms will also be reviewed by the ISMS and NYU PIs weekly to assess the need to reduce the dose or discontinue the medication.

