2.3 POTENTIAL RISKS AND BENEFITS

2.3.1 Potential risks. This study poses minimal risk to both patients and employees enrolled in the study. Loss of confidentiality is the greatest potential risk to study subjects. All participants will receive an identification number that will be used for all forms, transcripts, surveys and intervention materials. For patients, we are using two behavioral interventions and nicotine gum. The nurse conducting enrollment will assess risk factors related to the use of nicotine replacement therapy (NRT) that would exclude patients from enrolling. Patients with a recent history of myocardial infarction (MI) (two weeks), serious underlying arrhythmias, and patients who are pregnant or nursing will not be offered NRT. It is important to note that the nicotine gum is an over-the-counter medication, with proven safety, and with minimal potential side effects. In addition, there are no significant interactions between NRT and HIV treatments (<http://www.hivdruginteractions.org/PrintableCharts.aspx>). Recent changes in FDA labeling also confirm that it is safe for tobacco users to use NRT while continuing to smoke. The FDA label for over the counter (OTC) NRT now says that: “concomitant use of OTC NRT products with cigarettes or with other nicotine-containing products does not raise significant safety concerns”. Employees in the participating health clinics will be asked to sign consent which will explain the voluntary nature of their participation and that they can withdraw their participation at any time without consequences in terms of risk to employment. Employee data will be treated as described above to ensure that their responses to survey questions and interviews remains confidential and cannot be linked to any employment records. The enrollment and consent procedures to ensure that there is no coercion are described below in section 12.1.

2.3.2 Potential benefits. Patients who receive the counseling and/or nicotine gum may quit using tobacco.

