5.2 EXCLUSION CRITERIA

5.2.1. Patient Exclusion Criteria The few individuals for whom there is a need for precaution in using NRT will be excluded

- recent myocardial infarction (2 weeks)
- serious underlying arrhythmias
- patients who are pregnant or nursing
- any patient who participated in the study during wave 1 at OPC site 1-5 and then transferred to OPC site 6-13 during wave 2

We will also exclude those who are unable to demonstrate capacity for consent and patients already enrolled in a tobacco use treatment program.

Our pilot data indicate that about half of tobacco users in these sites are dual users (cigarettes and waterpipe); only about 12% use waterpipe alone. VQUIT found that dual users who received VHW counseling had 6-month CO confirmed quit rates that were comparable to patients who used cigarettes only. Therefore, we will not exclude dual users. We will exclude waterpipe only users because the intervention is based on effectiveness data for dual and cigarette users and there is a lack of evidence for efficacy or effectiveness of NRT use in this population.

5.2.2. Employee exclusion criteria. Employees who are unwilling to sign consent will be excluded.

5.3 VULNERABLE SUBJECTS. Employees are considered a vulnerable population. Research staff who work for the research institute (ISMS) will be responsible for consenting employees. Research staff are trained to emphasize that participation is voluntary and employees' decision will not affect their job evaluation, promotions and work-related assignments.

5.4 STRATEGIES FOR RECRUITMENT.

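### Sections 5.2.1 and 8.1 set conflicting cardiovascular entry criteria, most plainly a two-week against a four-week window after myocardial infarction

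*Combined protocol and SAP*

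**What the plan says.** Three places in the current protocol text deal with cardiovascular fitness for nicotine replacement therapy (NRT).

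- **Section 5.2.1, patient exclusion criteria.** The list opens with "The few individuals for whom there is a need for precaution in using NRT will be excluded". Its clinical items are "recent myocardial infarction (2 weeks"), "serious underlying arrhythmias" and "patients who are pregnant or nursing". Blood pressure and angina are not listed.
- **Section 2.3.1, potential risks.** The enrolling nurse is to assess "risk factors related to the use of nicotine replacement therapy (NRT) that would exclude patients from enrolling". The next sentence names the conditions and the result: "recent history of myocardial infarction (MI) (two weeks), serious underlying arrhythmias, and patients who are pregnant or nursing will not be offered NRT".
- **Section 8.1, specification of safety parameters.** "Patients with a recent history of MI (four weeks), uncontrolled hypertension, arrhythmia, or worsening angina pectoris will not be eligible to enroll". The same paragraph fixes the timing: "Eligibility for NRT will be assessed at the time study eligibility is assessed and prior to enrollment".

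No section says which statement governs. Section 13.3 requires protocol deviations to be documented and reported to the IRB.

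**The concern.** These are the protocol's own safety-related entry rules. They act at one decision, taken once per patient by a clinic nurse before consent and randomisation. If two sections give different answers for the same patient, staff can follow one and breach the other.

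Following 5.2.1 alone admits some patients whom 8.1 bars. Because the criteria apply before randomisation, such a patient could go to any arm, including the arm that receives gum. A monitor who checks the enrolment afterwards would have no agreed standard: it is proper under one section and improper under the other, so its status under 13.3 is unclear.

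**Working it through.** No power, sample size or error rate is involved, so the check is an item-by-item comparison. I read each MI window as meaning an infarction within the stated period.

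| Item | 5.2.1 | 2.3.1 | 8.1 | 5.2.1 against 8.1 |
|---|---|---|---|---|
| MI window | 2 weeks | 2 weeks | 4 weeks | Conflict |
| Arrhythmia | Serious underlying only | Serious underlying only | Any, no qualifier | Conflict |
| Uncontrolled hypertension | Not listed | Not listed | Bars entry | Differs |
| Worsening angina | Not listed | Not listed | Bars entry | Differs |
| Pregnant or nursing | Excluded | Not offered NRT | Not mentioned | Omission, not a conflict |

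**Step 1: do the lists act at the same point?** Yes. Section 5.2.1 is an enrolment rule. Section 8.1 speaks of eligibility to enrol and places the NRT assessment alongside the study eligibility assessment. They cannot be separated into an entry rule and a later treatment rule.

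**Step 2: how many items differ?** Four, all cardiovascular. Pregnancy and nursing are left out of the count. Section 8.1 is silent on them and does not claim to be complete, and section 8.4.4 repeats that pregnant women are excluded.

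**Step 3: how firm is each difference?**

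- *MI window.* Explicit in both places. The disputed interval runs from 2 to 4 weeks after the event: 28 − 14 = 14 days. No reading of the text makes the two figures agree.
- *Arrhythmia.* 5.2.1 carries a severity qualifier and 8.1 does not. A non-serious arrhythmia meets no listed exclusion in 5.2.1 and is barred by 8.1.
- *Hypertension and angina.* Neither is listed in 5.2.1. The opening sentence of that list is general enough that it might be read to cover them, so these two differences are softer.

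**Step 4: a worked case.** Take an MI 3 weeks before screening. Under 5.2.1, 3 > 2, so no listed exclusion applies. Under 8.1, 3 < 4, so the patient is barred. If 5.2.1 is followed, the patient can be randomised. With 16 of 48 patients per site planned for each arm, the chance of the gum arm is 16/48 = 1/3.

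**Step 5: wording within 2.3.1.** One sentence treats the risk factors as barring enrolment; the next says that such patients do not get NRT. The two are compatible, since an excluded patient is not offered gum, but the consequence should be worded the same way throughout.

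**The case against.** The strongest reply is that 5.2.1 obviously governs. It is the natural home for exclusions, 2.3.1 agrees with it on MI and arrhythmia, and the version 6.0 entry in the amendment log records that uncontrolled hypertension and unstable angina were deleted. A reader might infer that 8.1 is simply old wording and can be ignored.

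The documents do not support going that far. The log describes superseded text and is context only. Its visible rows, versions 6.0 to 9.0, do not mention the MI window or the arrhythmia qualifier, and any earlier rows cannot be seen, so that silence carries little weight either way. Its angina term (unstable) is not the one in 8.1 (worsening). Meanwhile 8.1 stands in the current text as an unqualified bar to enrolment, and nothing gives 5.2.1 precedence.

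A second reply is that the general opening of 5.2.1 already takes in the extra conditions. That has some force for hypertension and angina, which is why they are ranked below the MI window. It cannot turn two weeks into four.

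A third is that clinic staff worked from the screening form, not from the protocol sections. That may be so. The form is not in the public file, which is no fault of the plan, so the list actually applied cannot be verified here.

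Finally, risk is limited by other provisions: only the third arm receives gum, and side effects are assessed at each counselling visit. That bears on the likely harm. It does not resolve which patients may enter.

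**Conclusion.** The inconsistency is real and lies wholly in current text. Four cardiovascular items differ between 5.2.1 and 8.1. The MI window is a direct contradiction, the arrhythmia qualifier is a clear difference, and hypertension and angina are differences that a generous reading of 5.2.1 could narrow. The wording of 2.3.1 is a minor point. Because the rules concern safety at entry, and the correction is cheap, it should be made.

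Four stronger readings are tempting and not supported:

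- *That barred patients were enrolled.* The documents give no prevalence and no screening data, so no count can be stated.
- *That the arm comparison is biased.* Both lists apply before randomisation and to all three arms alike.
- *That the sections also conflict on pregnancy and nursing.* Section 8.1 merely omits them.
- *That 2.3.1 lets at-risk patients enter without gum.* Its preceding sentence, 5.2.1 and 8.1 all speak of exclusion from enrolment.

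The conclusion assumes only that both sections are in force as printed.

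**What to change.** The clinical investigators should reconcile sections 2.3.1, 5.2.1 and 8.1 to one list with one stated consequence. The list should stand once, in 5.2.1, with cross-references from the other two sections. They should then confirm that the nurse screening form, on paper and in REDCap, carries that list. Which criteria are right, and whether the consequence is exclusion or no offer of NRT, is for them to decide; none is proposed here.

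Optionally, they can record in a dated note which list the form used. Any look-back would be limited to items already recorded: a form that asked only about MI within two weeks cannot identify one at three weeks, and the note should then say so.

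The cost is wording in three sections and one check of the screening form. No new patient contact, procedure or analysis is needed.
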